### 9.2. Setting

The study population will be obtained from a local registry, including patients diagnosed with moderate-to-severe plaque psoriasis and have been receiving etanercept treatment for at least 1-year. Study population must be  $\geq 18$  years of age and have difficult to treat sites at presentation.

#### 9.2.1. Inclusion Criteria

Patients must meet each of the following inclusion criteria to be eligible for inclusion in the study:

1. Moderate-to-severe plaque psoriasis patients who have been receiving etanercept for at least 1-year duration.
2. Have difficult to treat sites at presentation.
3. Age  $\geq 18$  years.
4. No history of using other biological treatments, other than etanercept for the treatment of moderate-to-severe PsO.

PFIZER CONFIDENTIAL

### **9.2.2. Exclusion Criteria**

Patients meeting any of the following criteria will not be included in the study:

1. Etanercept use for treatment of moderate-to-severe PsO less than 1-year duration.
2. Previous use of another biological treatment for treatment of moderate-to-severe PsO.

### **9.3. Data Sources**

The data source will be from local registry at Dermatology Center of Baghdad Teaching Hospital. The data are structured and will be analyzed by the investigator.

### **9.4. Study Size**

This study will include approximately 400 patients from the registry that meet the inclusion criteria of having moderate-to-severe PsO with difficult to treat sites at presentation.

### **9.5. Data Management**

Data already exists in a structured format and will be extracted to an excel spreadsheet which will be analyzed using the SPSS database (version 23).

### **9.6. Data Analysis**

Detailed methodology for summary and statistical analyses of data collected in this study will be documented as below.

All covariates will be summarized to get information about frequency distribution and mean, median or standard deviation. Numbers and percentages will be provided for dichotomous and polychotomous variables when performing descriptive analysis of categorical data. Means, medians, standard deviations and interquartile range as appropriate will be provided for continuous variables when performing descriptive analysis of continuous data.

The bivariate analysis will be conducted to determine if there is any association between the outcome and the exposure (the covariates). Unadjusted comparisons of baseline characteristics for 0, 4, and 12 months after treatment and last visit disease activity index against outcome measures will be provided. Appropriate tests will be used based on the distribution of the measure: chi-square test will be used for categorical variables, t-test will be used for continuous variables, and the Kruskall-Wallis test for non-parametric variables; p-values will also be generated.

No regression model will be built for this analysis.

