## 8. RESEARCH QUESTION AND OBJECTIVES

This study aims to see the efficacy of Enbrel as a biological treatment for PsO in Iraqi patients who have difficult to treat sites at presentation.

**Primary objective:** Efficacy of Enbrel in plaque psoriasis with difficult to treat sites by measuring the following baselines: BSA, PASI and DLQI. A comparison between 6 months after treatment and last visit follow-up will be analyzed.

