**Secondary objective:**

Determine the adherence of patients to the biological treatment.

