## 9. RESEARCH METHODS

### 9.1. Study Design

This is a retrospective analysis of approximately 400 patients that were diagnosed with moderate-to-severe plaque psoriasis with difficult to treat sites. Patients will receive Enbrel as treatment for their disease and will include primary and secondary endpoints.

**Primary objective:** Efficacy of Enbrel in Moderate-to-Severe Plaque Psoriasis with difficult to treat sites by measuring the baselines of BSA, PASI and DLQI and compare it with 6 months after treatment and last visit follow-up during study.

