**Secondary objective:**

- Determine the compliance of patients with Moderate-to-Severe Plaque Psoriasis on Enbrel.
- Will take the baselines of BSA, PASI and DLQI for 6 months after treatment and last visit disease activity index to see the efficacy.
- The patients will be divided into 2 groups according to their adherence to Enbrel. and will be compared between both groups in BSA, PASI and DLQI at 6 months after treatment and last visit disease activity index.

Also the demographic characterization of patients will be obtained (patients age, gender, disease duration, etc.) during data collection.

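### Section 9.6 analyses 0, 4 and 12 months and last visit, so the 6-month time in the primary objective and the adherence-group comparison has no planned analysis

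*Combined protocol and SAP*

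**What the plan says.** **Objectives.** Section 9.1 gives the primary objective as "measuring the baselines of BSA, PASI and DLQI and compare it with 6 months after treatment and last visit follow-up during study". Section 8 words it differently: after naming the three measures at baseline, it says "A comparison between 6 months after treatment and last visit follow-up will be analyzed".

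Two secondary bullets in Section 9.1 also name 6 months. The efficacy bullet reads "Will take the baselines of BSA, PASI and DLQI for 6 months after treatment and last visit disease activity index to see the efficacy". For adherence, "The patients will be divided into 2 groups according to their adherence to Enbrel", and these "will be compared between both groups in BSA, PASI and DLQI at 6 months after treatment and last visit disease activity index". Section 8 states the adherence objective with no time: "Determine the adherence of patients to the biological treatment".

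**Analysis.** Section 9.6 presents itself as the detailed methodology. Its only statement of times is "Unadjusted comparisons of baseline characteristics for 0, 4, and 12 months after treatment and last visit disease activity index against outcome measures". On tests it says "Appropriate tests will be used based on the distribution of the measure", then names chi-square for categorical variables, a t-test for continuous variables and Kruskal-Wallis for non-parametric variables. It rules out any regression model.

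**Other places that might bridge the two.** Section 4 defers the abstract to Annex 1, which lists a stand-alone document that is not reproduced. The one-year period in Sections 9.2, 9.2.1 and 9.2.2 is a minimum exposure for eligibility, not an assessment time.

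**The concern.** The fixed follow-up time in the primary objective is missing from the section that says what will be analysed. Followed as written, Section 9.6 gives results at 4 and 12 months and none at 6 months. The 6-month primary comparison would then be omitted or be run outside the written plan. A report led by month 4 or 12 would contradict the objective; one led by month 6 would not follow the analysis section.

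This matters more because the data already exist. With three candidate times (4, 6 and 12 months) and no rule saying which section controls, the reported time could be chosen with results in view, and a reader could not tell.

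Timing limits what rewording can achieve. Section 6 shows data collection ending on 01 August 2020 and prints 2020 as the actual date of the final report, although the planned date is 30 Jun 2021. The 10 June 2021 entry in Section 5 speaks of alignment with a study report. A report may therefore already exist, although the text does not settle this. Rewording alone would not tell readers which times were used.

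**Working it through.** **1. Times side by side**

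| Time | Section 8 primary | Section 9.1 primary | Section 9.1 efficacy bullet | Section 9.1 adherence groups | Section 9.6 |
|---|---|---|---|---|---|
| Baseline (0) | yes | yes | yes | not named | yes |
| 4 months | no | no | no | no | yes |
| 6 months | yes | yes | yes | yes | **no** |
| 12 months | no | no | no | no | yes |
| Last visit | yes | yes | yes | yes | yes |

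The objectives' follow-up times are {6 months, last visit}. Those of Section 9.6 are {4 months, 12 months, last visit}. The only shared follow-up time is last visit.

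**2. Contrasts affected**, reading Section 9.6 as applying to BSA, PASI and DLQI:

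- Primary objective (Section 9.1): 3 measures × 2 follow-up times = 6; absent from Section 9.6: 3 × 1 = 3.
- Adherence groups: 3 × 2 = 6; absent: 3 × 1 = 3.
- Section 9.6: 3 × 3 = 9; with no matching objective (4 and 12 months): 3 × 2 = 6.

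**3. Section 8 against Section 9.1.** Read literally, Section 8 compares 6 months with last visit, while Section 9.1 compares baseline with each. The first measures whether response is maintained; the second measures response. No section says which controls. Both need 6 months.

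**4. Secondary point: paired data.** Change from baseline is a within-patient quantity. Section 9.6 does not say that its t-test is paired, and Kruskal-Wallis is for independent groups. Kruskal-Wallis can serve the two adherence groups but not within-patient change.

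The illustration below takes 400 patients (Section 9.4). It assumes normal data, equal SD at both visits, two-sided alpha 0.05 and within-patient correlation ρ of 0.3, 0.5 or 0.7. The documents give none of these assumed values.

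Standard error of the mean change, in SD units:

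- Unpaired: √(2/400) = 0.0707.
- Paired: √(2(1 − ρ)/400) = 0.0592, 0.0500, 0.0387.
- Ratio: 1/√(1 − ρ) = 1.20, 1.41, 1.83.

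Share of simulated studies that reject (4,000 per cell):

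| ρ | Kruskal-Wallis, change 0.1 SD | Signed-rank, change 0.1 SD | Kruskal-Wallis, no change | Signed-rank, no change |
|---|---|---|---|---|
| 0.3 | 0.257 | 0.383 | 0.018 | 0.046 |
| 0.5 | 0.221 | 0.510 | 0.006 | 0.051 |
| 0.7 | 0.154 | 0.719 | 0.001 | 0.044 |

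Under these assumptions, ignoring the pairing loses power and precision; it does not produce false positives.

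**The case against.** **The sentence in Section 9.6 is too loose to support the counts.** It speaks of baseline characteristics against outcome measures, in a paragraph about covariates and outcome. It names neither the three measures nor the adherence groups. This stands as a qualification: the counts hold only if the sentence is read as the analysis of the objectives. Read strictly, none of the 6 primary or 6 adherence-group contrasts is explicitly specified, which is no better for the plan. No reading supplies a 6-month analysis.

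**Sections 8 and 9.1 may mean the same thing.** Section 8 mentions baseline just before the comparison, so it can be read as baseline against each follow-up. That is a fair reading of loose drafting, but the literal one is also open and the two give different contrasts.

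**The paired-test point is separate and rests on assumed values.** The unqualified term t-test does not exclude a paired test. A large fall from baseline would probably be significant either way. Both are true. The loss falls mainly on precision and on small contrasts such as 6 months versus last visit, and the main finding does not depend on it.

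**The history is unclear.** The 28 May 2021 log entry cites Section 8.6, which matches the present Section 9.6 by title only, and records template alignment. It does not show when the 0, 4 and 12 month wording entered. That remains a question to the sponsor, not a finding.

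**The study is descriptive and the remedy light.** It is retrospective, with no stated power calculation and no regression model. This limits the consequence, but a primary time absent from the only analysis section remains a contradiction in current text.

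**Conclusion.** The concern holds and must be fixed. The plan is inconsistent as written, which is more than a lack of detail. Six months is named in both statements of the primary objective and in two secondary bullets, and Section 9.6 does not contain it. Nothing in the supplied text maps one set of times to the other or shows which was intended.

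The mismatch itself rests on the text alone. Its size, half of the primary and half of the adherence-group contrasts without a planned analysis and two thirds of the Section 9.6 follow-up contrasts without an objective, is conditional on reading Section 9.6 as applying to BSA, PASI and DLQI. The paired-test point is secondary, and its figures are illustrative.

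**What to change.** 1. Check first which assessment times the registry extract holds; the supplied text does not show this.
2. If 6-month assessments exist, make Section 9.6 read baseline, 6 months and last visit. If they do not, restate the objectives at the times held and label that change post hoc.
3. Reconcile Section 8 with Section 9.1. If 6 months versus last visit is also wanted, list it as a separate paired contrast.
4. State the primary analysis as within-patient change in BSA, PASI and DLQI from baseline to each follow-up time, by paired t-test or Wilcoxon signed-rank test. Compare the two adherence groups at the same times with independent-group tests.
5. Date the change. In the study report, disclose which times were analysed and why, with results at all available times. Any retained 4- and 12-month results should be labelled as supplementary. Say whether the 0, 4 and 12 month wording came in with the 28 May 2021 change to the Data Analysis section.
6. If a report has already been issued, disclose by correction or addendum. Section 11.3 requires prospective approval of amendments, and an amendment made after the report could not be prospective for that analysis.

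**Cost:** a check of the extract, a small reanalysis, and a dated amendment or report disclosure. The time point may have to carry a post hoc label. No new data collection is needed.

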## **9.8. Limitations of the Research Methods**

The missing data that could lead to bias is an identified limitation in this study.

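### Section 9.6 assigns no paired test to the within-patient primary comparisons of BSA, PASI and DLQI; applied to skewed scores across visits, its distribution-only rule would lose power for small changes

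*Combined protocol and SAP*

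**What the plan says.** Section 9.1 states the primary objective as "measuring the baselines of BSA, PASI and DLQI and compare it with 6 months after treatment and last visit follow-up during study". Section 8 adds "A comparison between 6 months after treatment and last visit follow-up will be analyzed". There is one cohort of about 400 patients, all on Enbrel, so both are comparisons of a patient with himself or herself.

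Section 9.6 is the only analysis section. It opens its testing plan with associations between outcome and covariates, then lists "Unadjusted comparisons of baseline characteristics for 0, 4, and 12 months after treatment and last visit disease activity index". The selection rule follows: "Appropriate tests will be used based on the distribution of the measure". The tests named are chi-square for categorical variables and, for the rest, "t-test will be used for continuous variables, and the Kruskall-Wallis test for non-parametric variables". It closes with "No regression model will be built for this analysis".

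One planned comparison is between different patients. Under the secondary objective in Section 9.1, "The patients will be divided into 2 groups according to their adherence to Enbrel".

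Section 9.8 gives a single limitation: "The missing data that could lead to bias is an identified limitation in this study".

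**The concern.** The choice of test should depend first on whether the compared scores come from the same patients, and only then on distribution. Section 9.6 uses distribution alone. The t-test exists in paired and unpaired forms, so roughly normal scores may be covered. Kruskal-Wallis has no paired form: it assumes independent observations. An analyst who follows the rule literally with skewed BSA, PASI or DLQI would compare visits as if they came from different people. No signed-rank, Friedman or other repeated-measures procedure is offered as an alternative, and modelling is ruled out.

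At stake is the ability to see a small within-patient change. The most exposed comparison is 6 months against last visit, where a modest loss of response could give a non-significant result and be read as a maintained one. Section 9.6 plans means and medians but no confidence interval for the change, so the reader could not judge how much drift remains compatible with the data. The plan also does not say how a patient missing one of the two compared visits is handled.

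**Working it through.** **Inputs.** From the documents: about 400 patients (Sections 9.1 and 9.4), one cohort, repeated scores, and the tests listed in Section 9.6. The plan gives no power, significance level, SD, within-patient correlation or number of complete pairs, so it has no figure to reproduce. Assumed here: two-sided 5%, n = 400 complete pairs, correlation ρ = 0.3, 0.5 or 0.7.

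**Step 1: true size when pairing is ignored.** With equal SDs, the mean change has true standard error SD·√(2(1−ρ)/n). An unpaired test uses SD·√(2/n), which is too large when ρ > 0. Its true size is 2·[1 − Φ(1.96/√(1−ρ))]:

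- ρ = 0.3: 1.96/0.837 = 2.34, size 1.9%
- ρ = 0.5: 1.96/0.707 = 2.77, size 0.56%
- ρ = 0.7: 1.96/0.548 = 3.58, size 0.03%

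Simulated Kruskal-Wallis on lognormal scores with no true change rejects in 2.1/0.7/0.0%, which agrees.

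If the later SD is k times the baseline SD, the multiplier of 1.96 becomes √((1+k²)/(1+k²−2ρk)). At k = 0.5 the size is 2.5/1.1/0.31%. For three visits tested together with equal SDs and correlations, P(χ² on 2 df > 5.991/(1−ρ)) = 1.4/0.25/0.005%. The direction is the same throughout: conservative.

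**Step 2: smallest shift detected with 80% power, normal scores.** Paired: (1.96 + 0.84)·√(2(1−ρ)/400). Unpaired: (1.96 + 0.84·√(1−ρ))·√(2/400).

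| ρ | Paired | Pairing ignored |
|---|---|---|
| 0.3 | 0.166 SD | 0.188 SD |
| 0.5 | 0.140 SD | 0.181 SD |
| 0.7 | 0.109 SD | 0.171 SD |

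**Step 3: power on skewed scores.** Simulated lognormal scores (log-SD 0.6), 400 complete pairs, shift of 0.15 in log-SD units, tests run on the unlogged scores.

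| ρ | Kruskal-Wallis | Paired t-test | Difference |
|---|---|---|---|
| 0.3 | 55% | 61% | 6 points |
| 0.5 | 57% | 75% | 18 points |
| 0.7 | 57% | 91% | 34 points |

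The signed-rank test gives 66/80/95% in the same setting. At a shift of 0.30 SD, Kruskal-Wallis and signed-rank both exceed 99%, so the choice no longer matters.

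**Step 4: what a confidence interval would show.** The 95% half-width for the mean change is 1.96·√(2(1−ρ)/m) SD. For m = 400 pairs it is 0.12/0.10/0.08 SD; for m = 200 it is 0.16/0.14/0.11 SD.

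**The case against.** Section 9.6 brings in its tests for outcome-covariate associations, where independent-group tests are suitable, and Kruskal-Wallis is also valid for the two adherence groups. The sentence on visits is hard to parse and does not clearly attach any test to baseline against 6 months. BSA, PASI and DLQI could simply fall under the t-test, run as paired, and with about 400 patients that would be reasonable despite moderate skew. All of this stands. A reader might infer that the plan prescribes Kruskal-Wallis for the primary comparison; the text does not go that far. But if the listed tests apply only to covariates, the primary comparison has no test at all, so either reading calls for an amendment.

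It can also be said that the harm is bounded. The error is conservative, the gain from pairing is only about 6 points at a correlation of 0.3, and no important difference is stated against which to judge the loss. That stands too, and it limits the severity.

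**Conclusion.** The omission is certain: no paired test is assigned to the within-patient comparisons, and test choice rests on distribution alone. The harm is conditional on three things: scores skewed enough to trigger the non-parametric branch, that branch being applied across visits, and positive within-patient correlation. Then p-values are too large and power is lost at small shifts, from 6 to 34 percentage points at 0.15 SD under the assumptions shown.

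A reader might infer that the efficacy finding itself is unsafe. It is not, on this ground. With positive correlation, ignoring the pairing cannot manufacture a benefit, and a large change from baseline would still be detected. The concern is mainly 6 months against last visit.

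The correlations, SDs, distribution and 400 complete pairs are all assumptions. This should be fixed, at the low end of that grade.

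**What to change.** Amend Section 9.6 as follows.

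- Analyse each within-patient two-visit comparison of BSA, PASI and DLQI with a paired t-test, whatever the skewness. Report the mean within-patient change, its 95% CI and the number of complete pairs.
- Add the Wilcoxon signed-rank test with the Hodges-Lehmann estimate and its CI as a sensitivity analysis.
- Keep the independent t-test, Kruskal-Wallis and chi-square for comparisons between different patients (adherence groups, covariates). No regression model is needed.
- Reconcile the visit times so that the contrasts are defined: Sections 8 and 9.1 use 6 months, Section 9.6 uses 0, 4 and 12 months.

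Do not switch tests on a skewness cut-off, and do not set a signed-rank p-value beside a median change. Signed-rank assumes symmetric changes. In a simulation with the later log-SD halved and a true median change of zero, a rule switching to signed-rank above a skewness of 1 rejected in 49/59/68% at correlations 0.3/0.5/0.7. The mean does change there, so these are not false positives about the mean, but the p-value would not describe the median reported with it.

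**Cost.** A small rerun on existing data, with no new collection. The change must be labelled post hoc, because data collection ended on 01 August 2020 (Section 6). The amendment needs IRB/IEC approval (Section 11.3). Any results already reported need updating; the amendment table in Section 5 refers to an existing study report.

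### Two non-randomised adherence groups are compared with unadjusted tests only, so confounding by baseline factors that are collected may remain and no adjusted estimate is planned to check it

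*Combined protocol and SAP*

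**What the plan says.** The secondary objective in section 9.1 of the combined protocol and SAP states: "The patients will be divided into 2 groups according to their adherence to Enbrel". It adds that they "will be compared between both groups in BSA, PASI and DLQI at 6 months after treatment and last visit disease activity index". Section 8 words the secondary objective more narrowly: "Determine the adherence of patients to the biological treatment".

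The covariates needed for an adjusted comparison are collected. The primary objective in 9.1 relies on "measuring the baselines of BSA, PASI and DLQI and compare it with 6 months after treatment and last visit follow-up during study", so baseline severity is available. Section 9.1 also says that "the demographic characterization of patients will be obtained (patients age, gender, disease duration, etc.) during data collection".

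For analysis, section 9.6 says: "The bivariate analysis will be conducted to determine if there is any association between the outcome and the exposure (the covariates)". It describes its comparisons as unadjusted, names the chi-square, t and Kruskal-Wallis tests, adds that "p-values will also be generated", and closes with "No regression model will be built for this analysis". Section 9.8 lists missing data as the only limitation.

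**The concern.** Adherence is not assigned at random. If patients who adhere differ at baseline in severity, age, gender or disease duration, a difference between the groups at follow-up, or the lack of one, may partly reflect who adheres. The reader would get a p-value and no adjusted figure to set beside it. This is a stated rule, not missing detail: regression is excluded without exception, and no stratification, matching, weighting or change-from-baseline comparison between the groups is described elsewhere. Section 9.6 does not name the adherence comparison, but no other section says how to analyse it.

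**Working it through.** **What the documents supply.** They give about 400 patients (9.1, 9.4), two groups, three measures and two time points (9.1). They give no SD, correlation, baseline imbalance, adherence split or significance level, so there is no figure of the plan's own to reproduce. Everything below is illustrative.

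**Assumptions.** N = 400, all analysed; two-sided 5% test; within-group SD of 1; no true adherence effect; baseline-outcome correlation ρ of 0.3, 0.5 or 0.7; group means of the baseline value differing by d SD; splits of 200:200 and 320:80.

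**1. Bias and rejection rate of the crude test.** Bias = ρ × d. SE = √(1/n₁ + 1/n₂), which is 0.100 at 200:200 and 0.125 at 320:80. The rejection rate comes from the noncentral t distribution with 398 degrees of freedom and noncentrality bias/SE. Example: ρ = 0.5 and d = 0.2 give a bias of 0.10 SD. Noncentrality is 0.10/0.100 = 1.00 at 200:200 (16.9% rejection) and 0.10/0.125 = 0.80 at 320:80 (12.6%).

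| d (SD) | 200:200, ρ = 0.3 / 0.5 / 0.7 | 320:80, ρ = 0.3 / 0.5 / 0.7 |
|---|---|---|
| 0.1 | 6.0 / 7.9 / 10.7% | 5.7 / 6.8 / 8.6% |
| 0.2 | 9.2 / 16.9 / 28.7% | 7.7 / 12.6 / 20.1% |
| 0.5 | 32.2 / 70.3 / 93.7% | 22.4 / 51.4 / 79.8% |

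At a weaker correlation the issue nearly vanishes: ρ = 0.1 and d = 0.2 give a bias of 0.02 SD and 5.5% rejection at 200:200.

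**2. Does baseline adjustment hold up with skewed scores?** Outcomes were simulated with 30% or 50% of the reference group at a floor of zero (splits 200:200, 320:80 and 80:320; d = 0.2 and 0.5; 36 settings, 4,000 datasets each). ANCOVA with robust (HC3) standard errors rejected in 4.3–5.8%, with bias of at most 0.024 SD. The crude t-test rejected in 6.0–91.3%. Baseline was the only confounder in these runs.

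**3. Precision.** With one covariate, the ANCOVA variance relative to the crude variance is f = (1 − ρ²) × [1 + d²/((N − 2)(1/n₁ + 1/n₂))]. The precision gain is cancelled once missing covariates remove more than a fraction 1 − f of patients.
- With d = 0, f = 0.91 / 0.75 / 0.51, so the tolerable loss is 9 / 25 / 49%.
- With d = 0.5, ρ = 0.3 and 200:200, f = 0.91 × (1 + 0.25/3.98) = 0.967, so the tolerable loss is 3.3%.
- At ρ = 0.3 there is no gain at all once d exceeds 0.63 SD (200:200) or 0.78 SD (320:80).

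The model proposed below has further covariates, and imbalance in those would lower the tolerable losses; that was not calculated.

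**4. What ANCOVA does not repair.** A simulation (balanced baseline, no adherence effect on outcome) let adherence depend on response, with a latent correlation of 0.1 with the baseline-independent part of response. Bias was the same with and without adjustment, about 0.11–0.15 SD. At ρ = 0.3 / 0.5 / 0.7 the crude test rejected in 34 / 25 / 21% and ANCOVA in 37 / 34 / 34%; a repeat check gave a similar pattern. Adjustment leaves reverse causation in place and can make it look firmer.

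**The case against.** The strongest reply is that 9.6 sets out to test for association and calls its comparisons unadjusted. If baseline differs by adherence, mean outcomes do differ between the groups, and rejecting equality is then correct. A reader might infer from the table that the planned test has a false-positive rate of up to 94%. The documents do not support that: no section states that the p-value estimates an effect of adherence, and every input to the table is assumed. This part of the objection stands.

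A reader might also infer that the groups are known to differ, or that the efficacy result is compromised. Neither follows. No baseline data by adherence are shown, and the primary comparison is within patients.

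It is also fair to say that the precision argument is weak, that ANCOVA cannot deal with reverse causation, and that the entry criteria raise a selection problem it need not solve. Sections 9.2 to 9.2.2 require at least one year of etanercept, so anyone who stopped earlier is excluded, on a condition met only after the 6-month outcome. A baseline table by group and a fuller limitations section would be cheaper still.

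The objection does not remove the gap. The comparison is listed among secondary objectives, next to a bullet that refers to efficacy, and it carries p-values. The covariates are in hand, and a table alone would show an imbalance without showing how much it matters.

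**Conclusion.** The point holds as a limited one. Section 9.1 plans a comparison of non-randomised groups, and 9.6 rules out the adjusted estimate that would let a reader check it against measured baseline differences. Confounding may remain; it is not demonstrated. Its size depends on correlation, imbalance and split, none of which the documents give, and under the assumed ranges it runs from negligible to large. The crude comparison remains valid as a crude association. Precision is not a main reason for the change. The reach is one bullet of a secondary objective that section 8 states more narrowly. The change should be made, with medium confidence, but nothing in the primary analysis depends on it.

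**What to change.** By dated amendment to 9.6, keep the unadjusted comparisons, limit the no-regression sentence to them, and add:

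- A definition of the two adherence groups, fixed before any model is fitted. The documents give none.
- Baseline characteristics tabulated by adherence group.
- For each of BSA, PASI and DLQI, at 6 months and at last visit, a supplementary linear model (ANCOVA) with robust or bootstrap standard errors, containing adherence group, the baseline value of the same measure, age, gender and disease duration.
- The adjusted difference with 95% CI, beside the unadjusted difference both in all available patients and in the same complete cases, each with its n, described as an association.

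Label the adjusted analysis post hoc if results have been seen. This is likely: section 6 ends data collection on 01 August 2020 and gives 2020 as the actual report date, and section 5 records a 10 June 2021 amendment made to agree with the study report.

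In 9.8, add confounding, reverse causation (response driving adherence, which ANCOVA does not remove and may make look more precise) and selection from requiring at least one year of etanercept.

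Separately, the time points in 9.6 (0, 4 and 12 months) must be reconciled with the 6 months in sections 8 and 9.1; this adds no weight to the present point.

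**Cost.** A few lines of text, one table and six models (3 measures × 2 time points) on variables already collected, in the SPSS already planned (9.5). Patients with a missing covariate drop out of the adjusted model, and missing data is the one limitation the protocol names. A post-hoc label lowers the weight of the adjusted result.
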